14/6/2025

NCT: 05893823

Retrospective study on radiological factors predictive of symptomatic psoas impingement development in protruding cups in primary hip arthroplasty

INTRODUCTION

Groin pain after total hip arthroplasty (THA) is a relatively rare condition, with reported incidence ranging from 0.4% to 18.3%. The most common intrinsic causes of groin pain include infection, aseptic loosening, impingement, and fractures. Iliopsoas (IP) tendinopathy following THA is an insidious and often underdiagnosed condition, affecting between 0.37% and 4.3% of implanted hips.

IP tendinopathy arises from friction, irritation, and mechanical stress on the tendon, often due to impingement. Both direct and indirect causes have been identified. In press-fit acetabular components, direct causes include prominent or malpositioned cups, lack of anterior bony coverage, and screw protrusion. Indirect causes, such as increased offset and leg length discrepancy, have been inconsistently reported in the literature.

Acetabular cup protrusion on axial imaging has been identified as the most sensitive and specific predictor of symptomatic IP impingement. However, cup prominence is also frequently seen in asymptomatic THAs. According to the literature, other radiological parameters—beyond cup prominence—may influence or predict the onset of IP impingement. Thus, cup protrusion alone seems to be a necessary but not sufficient condition for the development of IP tendinopathy.

The aim of this study is to compare a retrospective cohort of patients with acetabular cup protrusion who did not develop symptoms compatible with IP tendinopathy, with a group of patients who did present with symptomatic cup prominence and were treated with arthroscopic IP tenotomy. Post-THA CT scans were analyzed to identify which radiological or positional factors (e.g., inclination, version, offset, leg length discrepancy, and reaming technique) could predict the onset of IP impingement in patients with prominent acetabular cups.

OBJECTIVES, STUDY DESIGN, AND POPULATION

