The objective of this study is to identify post-operative CT-based radiological predictors of symptomatic IP tendinopathy in patients with acetabular cup prominence. The analysis compares asymptomatic and symptomatic patients, the latter having undergone arthroscopic tenotomy for IP tendinopathy. All patients were treated at the IRCCS Istituto Ortopedico Rizzoli, Department of Orthopaedics, Trauma and Hip/Knee Arthroplasty and Revision Surgery, between 2000 and 2021.

This is a retrospective observational cohort study. The study population includes adult patients who underwent primary THA and subsequently had a post-operative CT scan performed for pain, clicking, or contralateral hip planning.

Inclusion criteria: primary THA, post-op CT scan available for pain, clicking or contralateral planning; minimum 5-year follow-up for the control group and history of IP tenotomy for the symptomatic group; complete clinical and radiological documentation.

Exclusion criteria: patient refusal; inadequate CT or CT performed for periprosthetic fracture, loosening, infection, or obvious wear; incomplete documentation; insufficient follow-up or resolved symptoms after conservative treatment.

ENDPOINTS AND OUTCOME MEASURES

The primary endpoint is the identification of CT-based radiological predictors of IP tendinopathy in patients with acetabular cup prominence after THA. These include acetabular version, inclination, offset, and reaming technique.

MATERIALS AND METHODS

This study evaluates the radiological predictors of symptomatic IP tendinopathy in a cohort of adults who underwent primary THA and exhibited acetabular cup prominence on post-operative CT. All patients were treated at the IRCCS Istituto Ortopedico Rizzoli between 2000 and 2021. Post-operative CT scans were reviewed, and cases with prominent acetabular cups were selected. Demographic, surgical, and follow-up data were retrieved from the medical records and routine clinical documentation.

Patients were stratified based on the presence or absence of IP tendinopathy. Symptomatic patients had to have undergone IP tenotomy after thorough diagnostic evaluation, including clinical tests, US-guided anesthetic injection (with failed response to multiple infiltrations), serial X-ray, CT, and lab testing to rule out other causes. This diagnostic workflow is supported by the international literature.

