The control group included patients with cup prominence who remained asymptomatic during at least 5 years of follow-up.

COLLECTED VARIABLES

Demographic variables: sex, age at primary THA, operated side, underlying diagnosis.

Implant-related variables: cup type and size, stem type, head diameter, bearing couple, time between THA and CT.

Cup prominence variables: axial and sagittal prominence in mm.

CT-based outcome measures:

- Acetabular version (°)
- Contralateral acetabular version (°)
- Version difference (°)
- Cup inclination (°)
- Femoral offset (mm)
- Acetabular offset (mm)

- Global offset (cm)
- Contralateral global offset (cm)
- Offset difference (cm)
- Acetabular diameter (mm)
- Diameter mismatch (mm)
- Eccentric reaming (mm)

Measurements will be validated through intra- and inter-observer reliability testing. Outcomes will be analyzed to identify radiological predictors of IP tendinopathy. The ultimate goal is to define intraoperative positioning strategies to reduce the risk of developing symptoms.

DATA ANALYSIS

Quantitative variables will be expressed as mean, standard deviation, minimum, and maximum values. Qualitative variables will be reported as frequencies and percentages. Inter- and intra-observer reliability will be assessed using correlation statistics with 95% confidence intervals and standard error. Differences between symptomatic and asymptomatic patients will be evaluated using the Mann-Whitney U test for continuous and discrete variables, and Chi-square test for categorical variables. All analyses will be performed using IBM SPSS version 25 or later. Statistical significance is set at $p < 0.05$.

STUDY TIMELINE

Start date: Date of Ethical Committee (EC) approval.

- Step 1: Kickoff meeting within 2 months of EC approval to plan the project phases, data collection, storage, analysis, and publication.
- Step 2: Data collection from month 2 to 12 post-kickoff.
- Step 3: Data analysis with involvement of all investigators.
- Step 4: Data publication.

End date: Within 18 months from EC approval (12 months for data collection, 6 months for analysis and publication).

DATA COLLECTION AND STORAGE

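### The plan contrasts tenotomy-treated IP tendinopathy with five symptom-free years, but its title, aim and goal claim predictors of symptom onset

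*Combined protocol and SAP*

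**What the plan says.** **Who is compared.** The inclusion criteria (Objectives, Study Design, and Population) ask for "minimum 5-year follow-up for the control group and history of IP tenotomy for the symptomatic group". Materials and Methods makes tenotomy a condition of being a case: "Symptomatic patients had to have undergone IP tenotomy after thorough diagnostic evaluation". The work-up listed there includes repeated infiltrations without success, so the cases are refractory as well as operated. The same section describes the other group: "The control group included patients with cup prominence who remained asymptomatic during at least 5 years of follow-up".

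**Who is left out.** The exclusion criteria end with "insufficient follow-up or resolved symptoms after conservative treatment". Symptomatic patients who neither resolved nor had tenotomy fit neither group definition.

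**What is claimed.** The title refers to the development of symptomatic impingement. The last sentence of the Introduction looks for factors that "could predict the onset of IP impingement in patients with prominent acetabular cups". The primary endpoint is predictors of IP tendinopathy, without restriction to operated disease. The paragraph closing Collected Variables adds: "The ultimate goal is to define intraoperative positioning strategies to reduce the risk of developing symptoms".

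**What is analysed.** Data Analysis plans Mann-Whitney and chi-square tests between the two groups. Nothing in the document counts, describes or analyses the excluded symptomatic patients, or limits the conclusion to operated disease.

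**The concern.** Two steps separate a control from a case: developing symptoms, and then going on to tenotomy rather than resolving. The claim concerns the first step, but the data show only the two combined. Patients who took the first step and not the second are the ones who could separate them, and they are excluded.

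The stake is the intended use. A factor related only to failure of conservative treatment, or to selection for surgery, could be reported as a predictor of onset and carried into positioning advice at primary THA. Conversely, a real onset factor could be missed if symptomatic patients who have it are less likely to reach tenotomy.

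**Working it through.** **1. Is there a figure to reproduce?** No. The document gives no sample size, effect size, SD or power. It puts IP tendinopathy at 0.37% to 4.3% of implanted hips, but gives no rate among prominent cups and no share of symptomatic patients who resolve or reach tenotomy. Everything numerical below is an illustration.

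**2. The logic.** Let X be a CT factor, S = 1 if symptoms develop, and T = 1 if a symptomatic patient reaches tenotomy.

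- Onset contrast (what is claimed): E[X | S=1] − E[X | S=0]
- Planned contrast: E[X | S=1, T=1] − E[X | S=0]
- Planned minus onset: E[X | S=1, T=1] − E[X | S=1]

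The last line is zero when T is unrelated to X among symptomatic patients. Estimating it needs symptomatic patients with T = 0, and the eligibility rules retain none. The assumption is therefore not testable within the study.

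**3. Direction and possible size.** Take X as standard normal, with P(S=1 | X) = expit(a + b₁X) and P(T=1 | S=1, X) = expit(c + b₂X). Here b₁ and b₂ are log odds ratios per SD, and a and c are set to give the assumed overall rates. Assumed inputs are:

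- onset 0.37%, 4.3%, 20% or 40% (the first two are the document's all-hip range, the others cover higher rates among prominent cups);
- share of symptomatic patients reaching tenotomy 10%, 25%, 50% or 75%;
- odds ratios per SD of 1, 1.5 or 1/1.5.

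Both contrasts were integrated numerically:

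| Odds ratio for onset | Odds ratio for tenotomy given symptoms | Onset contrast (SD) | Planned contrast (SD) |
|---|---|---|---|
| 1.5 | 1 | 0.39–0.41 | 0.39–0.41 |
| 1 | 1.5 | 0.00 | 0.10–0.36 |
| 1.5 | 1.5 | 0.39–0.41 | 0.49–0.76 |
| 1.5 | 1/1.5 | 0.39–0.41 | 0.04–0.31 |

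The results hardly change with the onset rate. The share reaching tenotomy drives them, and the discrepancy is largest when only 10% do.

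**4. Reading the table.** Row 1 is the favourable case, in which the planned contrast recovers the onset contrast. Row 2 is a difference with no onset effect behind it. Row 3 is a real onset effect that looks larger than it is, and row 4 is one that is partly or almost wholly hidden. The planned data cannot show which row applies to a given factor.

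**The case against.** **The contrast is declared, and it is a defensible choice.** The aim says openly that the comparator is "a group of patients who did present with symptomatic cup prominence and were treated with arthroscopic IP tenotomy", and the objective repeats it. The Introduction lists several causes of groin pain, so requiring a full work-up and surgery makes the cases more certain. This stands, and it is why the main comparison should stay. It does not justify the title, the onset sentence of the aim or the goal, which go beyond the declared contrast. The endpoint does not use the word onset, but it is still broader than the group studied.

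**A reader might infer that the study cannot say anything about onset.** The documents do not support that. If reaching tenotomy is unrelated to the CT factor among symptomatic patients, the planned contrast is the onset contrast. If one underlying severity drives both steps, the factor does predict onset and only the size of the difference is overstated. Association with tenotomy-treated disease can be estimated in any case.

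**A reader might also infer that comparing extremes must inflate the differences.** Row 4 of the table shows attenuation, so inflation is one possibility and not a rule.

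**Nor can a false-positive rate be attached.** Group sizes and the share reaching tenotomy are not given. Take an assumed 25 cases and 50 controls, a factor unrelated to onset, a log-odds of 0.4 or 0.8 per SD for tenotomy, and a tenotomy share of 30% to 70%. The Mann-Whitney rejection rate then runs from under 10% to over 50%. That range is too wide to describe this study.

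**Resolved patients are a less certain group.** The full work-up is required only of tenotomy cases, so some resolved patients may have had pain from another cause. The number with an adequate CT is also unknown. This stands, and it means that an analysis including them can support interpretation but should not decide which factors count as predictors.

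**Conclusion.** The point holds as a mismatch between the contrast studied and the conclusion claimed. It rests on the eligibility rules and group definitions, which are explicit, and on the absence of any text limiting the conclusion or examining the excluded symptomatic patients. An onset interpretation needs an unstated assumption that these data cannot check. The illustrative figures show only that the bias can run in both directions and need not be small; they do not estimate it for this study. The change should be made, because the results are meant to inform surgical positioning and the remedy leaves the main analysis as it is.

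**What to change.** 1. **Wording.** Restate the title, the onset sentence of the aim, the endpoint and the goal as factors associated with IP tendinopathy treated by tenotomy, compared with no symptoms over at least 5 years. Limit the conclusions, including any positioning advice, to that contrast. This can be done even if data collection is complete.

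2. **Excluded patients.** Keep the main comparison. Report how many prominent-cup patients were excluded because symptoms resolved, and how many symptomatic patients, if any, neither resolved nor had tenotomy. Where resolved patients have an adequate existing CT, measure it. Report two supportive comparisons with estimates and 95% confidence intervals: all symptomatic versus asymptomatic, and resolved versus tenotomy. The second addresses directly whether the factor is related to reaching tenotomy. Do not use either as a pass/fail rule for calling a factor a predictor.

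**Cost.** Some extra measurement of scans already on file, lower diagnostic certainty in the resolved group (to be stated as a limitation), and a narrower stated conclusion. If few resolved patients have an adequate CT, the supportive intervals will be wide; the counts and the restated wording are still worth having.

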Clinical data will be extracted from patient medical records and source documents. A standardized Case Report Form (CRF) will be used to collect relevant clinical and radiographic data. All data will be pseudo-anonymized using a unique patient code. The database will be stored in a password-protected computer accessible only to the investigators.

ETHICAL CONSIDERATIONS

The study protocol and all relevant documents will be submitted for approval to the competent authorities and Ethics Committee prior to study initiation. The study will comply with the principles of the most recent Declaration of Helsinki (Fortaleza, October 2013), as well as all applicable national and international regulations concerning clinical research. The protocol was written and the study will be conducted in accordance with ICH-GCP guidelines.

INFORMED CONSENT

As IRCCS Istituto Ortopedico Rizzoli is a recognized research institute, patient data used for research purposes are governed by Article 110-bis, paragraph 4 of the Italian Privacy Code (D.lgs 196/2003 as amended by D.lgs 101/2018). Therefore, specific consent for data processing is not required.

PRIVACY

All patients will be identified by a numerical code to ensure pseudo-anonymization. Data will be processed in compliance with current national and European privacy laws. Access to sensitive data will be restricted to study sponsors and designated personnel for monitoring/auditing purposes, the principal investigator and collaborators, the Ethics Committee, and relevant health authorities. Access to source documentation for audits or inspections will be granted while maintaining patient confidentiality.

FINAL REPORT AND PUBLICATION

The principal investigator commits to producing a final report and publishing the study results, regardless of outcomes, as described in the protocol. Any publication or dissemination (journals, conferences, seminars) will occur only after statistical processing and always in fully anonymous form.

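### Surgeon, approach and year of THA are not among the listed variables and only unadjusted tests are planned, so an operator or era imbalance could pass undetected as a CT predictor

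*Combined protocol and SAP*

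**What the plan says.** The section on objectives, design and population sets the span: "All patients were treated at the IRCCS Istituto Ortopedico Rizzoli, Department of Orthopaedics, Trauma and Hip/Knee Arthroplasty and Revision Surgery, between 2000 and 2021". The endpoint section names acetabular version, inclination, offset and reaming technique as the candidate predictors.

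Under Collected Variables the non-CT items are:

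- For the patient, "Demographic variables: sex, age at primary THA, operated side, underlying diagnosis", which gives no date of surgery.
- For the operation, "Implant-related variables: cup type and size, stem type, head diameter, bearing couple, time between THA and CT", which gives neither surgeon nor approach.
- For the protrusion itself, "Cup prominence variables: axial and sagittal prominence in mm".

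The CT measures follow. Materials and Methods adds a general statement: "Demographic, surgical, and follow-up data were retrieved from the medical records and routine clinical documentation". It does not say which surgical items are meant.

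Data Analysis plans Mann-Whitney tests for continuous and discrete variables and Chi-square tests for categorical ones, at p < 0.05. It plans no stratification, matching or regression. The use of the result is stated in Collected Variables: "The ultimate goal is to define intraoperative positioning strategies to reduce the risk of developing symptoms".

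**The concern.** Each candidate predictor is set wholly or largely by the person performing the index THA. Surgeon, approach and period can therefore plausibly shift cup position. They can also plausibly shift the chance of being classed as a case, because a case must have gone through a multi-step work-up, failed several infiltrations and had a tenotomy. A factor that acts on both sides of the comparison confounds it.

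If cases cluster in certain surgeons, approaches or years, the cup positions habitual there will differ between the groups even when position has no effect on symptoms. The planned tests would attribute that difference to position. Because the study intends to advise surgeons on positioning, the recommendation could then describe who operated, or when, and not what protects the tendon.

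**Working it through.** The documents give no sample size, group sizes, SDs or effect sizes, so there is no planned figure to reproduce. The check has three parts.

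**1. The lists.** Surgeon, approach and date or year of THA appear in none of the demographic, implant, prominence or CT lists, and are named nowhere else. Age at THA and the THA-to-CT interval do not give a calendar year when taken as variables.

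**2. Era imbalance from the eligibility rules.** Controls need at least 5 years of follow-up; cases need a history of tenotomy and have no such minimum. If follow-up closes at time F, a THA done after F minus 5 years can supply a case but not a control. F is not stated, so a range is shown, taking 2000–2021 (22 calendar years) as the THA dates:

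- F = end of 2021: THAs from 2017 to 2021 are case-only, 5/22 = 23% of the calendar span.
- F = mid-2025 (the date on the document): mid-2020 to end of 2021 is case-only, about 1.5/22 = 7%.
- F = end of 2026 or later: none.

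These are shares of calendar time, not of hips.

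**3. Size of the effect on the planned test (all inputs assumed).** Take two operators (or periods) whose mean CT measure differs by δ SD, with no link between the measure and symptoms within operator. Let operator A supply a share p1 of cases and p0 of controls. The spurious group difference is δ × (p1 − p0). With δ = 1 it is 0.2, 0.4 and 0.5 SD for shares of 60% vs 40%, 70% vs 30% and 80% vs 30%.

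Hand check for 30 cases, 60 controls, δ = 1, 70% vs 30%:

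- within-group SD = √(1 + 0.7 × 0.3) = 1.10
- standardised difference = 0.4 / 1.10 = 0.364
- expected z = 0.364 × √(30 × 60 / 90) = 0.364 × 4.472 = 1.63
- chance of p < 0.05 (two-sided assumed) ≈ P(Z > 1.96 − 1.63) ≈ 0.37

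Simulation of the Mann-Whitney test gives about 36% for that setting. Approximate simulated false-positive rates, 30 vs 60 (ranges reflect simulation error):

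| Operator difference | 60% vs 40% | 70% vs 30% | 80% vs 30% |
|---|---|---|---|
| 0.25 SD | 6% | 7% | 8–9% |
| 0.5 SD | 7% | 13–14% | 17–18% |
| 1 SD | 12–13% | 35–36% | 52% |

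With equal shares the rate stays at about 5%. A van Elteren rank test stratified by operator, run on the same data, stays near 5% in every cell.

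Other assumed sizes (20 vs 40, 50 vs 50, 50 vs 100; δ of 0.5 to 1) give 5.1–18.7% at 60% vs 40% and 10.6–54.9% at 70% vs 30%. The stratified test gives 3.9–6.0% throughout.

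**The case against.** Several points on the other side stand.

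- **Recoverability.** A reader might infer that operator and era effects can never be separated afterwards. The documents do not support that. "Clinical data will be extracted from patient medical records and source documents", patients carry a pseudonymous code, and nothing says the link to source is destroyed. The gap belongs to the dataset as listed and could be closed by re-extraction.
- **Not specified is not the same as not collected.** Unitemised surgical data are mentioned and the CRF is not shown, so the list may be incomplete. Year of THA is the weakest of the three items: deriving age at THA, the THA-to-CT interval and 5-year follow-up would ordinarily need the operation date. What is missing is its place as a named variable and any use of it in the analysis. Cup, stem and bearing type may also partly track era (an inference), though they do not identify surgeon or approach and nothing is adjusted for them.
- **Confounding is possible, not shown.** The number of surgeons, the approaches used and any imbalance are not given, and a single department may limit the variety. If a surgeon affects symptoms only through cup position, surgeon is a cause of the exposure and not a confounder, and stratifying discards useful variation. This argues for a sensitivity analysis and against a rule that denies a measure the label of predictor unless it persists within strata, particularly if tenotomy cases are few.
- **The illustration is assumed throughout.** The high rates need both a 1 SD difference and a marked imbalance. At 0.25 SD the inflation is small.

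The missing fields are also one part of a wider gap: no covariate is adjusted for, including those already listed. That does not remove the point, since an adjusted analysis could not use fields that were never recorded.

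**Conclusion.** The point holds as a gap in specification. Three variables closely tied to operator-delivered predictors are not listed for a series spanning about two decades, and no planned analysis would use them. Followed as written, the plan could report an operator, approach or era imbalance as a positioning predictor, and the listed variables would not reveal it. The follow-up rule, which binds controls only, makes some era imbalance plausible unless follow-up closes late enough for every THA to reach 5 years.

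The direction and size of any bias are unknown. The illustrative false-positive rates run from near nominal (about 6%) to about 52%. They rest on assumed group sizes, two operators, differences of 0.25 to 1 SD and the stated shares. It would go too far to say that the groups are in fact confounded or that the data cannot be repaired.

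**What to change.** 1. Add coded index surgeon, surgical approach and year of THA to the CRF and to the Collected Variables list, as far as the records hold them, and report how often each is missing. The documents do not confirm that surgeon and approach are available back to 2000.
2. Tabulate the three fields by group, and state the closing date of follow-up so that the case-only period is visible.
3. For each CT measure reported as a predictor, pre-specify a sensitivity analysis stratified by period and by surgeon or approach, for example a van Elteren test with low-volume surgeons pooled, as far as the number of tenotomy cases allows. Strata without both cases and controls contribute nothing, so report how many hips drop out for that reason.
4. Show crude and stratified results side by side, and say where an association cannot be separated from operator or era. Do not apply a fixed rule on what may be called a predictor.

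The cost is up to three more fields per hip (year is probably already at hand) and one further analysis. Precision falls where strata are small, and some crude associations may have to be reported as not separable from operator or era.

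### The plan does not say that CT readers are masked to symptom or tenotomy status, and its reliability testing cannot detect a group-linked bias that the readers share

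*Combined protocol and SAP*

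**What the plan says.** The Objectives section sets the comparison: "The analysis compares asymptomatic and symptomatic patients, the latter having undergone arthroscopic tenotomy for IP tendinopathy". The inclusion criteria there define cases by a past tenotomy and controls by at least 5 years of follow-up, so group membership exists before the study measurements.

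Under Endpoints and Outcome Measures, the primary endpoint is the set of CT-based predictors: "These include acetabular version, inclination, offset, and reaming technique". Materials and Methods describes the order of selection: "Post-operative CT scans were reviewed, and cases with prominent acetabular cups were selected", and then "Patients were stratified based on the presence or absence of IP tendinopathy".

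Two sentences deal with the quality of the readings. Collected Variables states: "Measurements will be validated through intra- and inter-observer reliability testing". Data Analysis adds: "Inter- and intra-observer reliability will be assessed using correlation statistics with 95% confidence intervals and standard error". Neither mentions masking, reading order or separation of readers from clinical data.

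The nearest text to masking is in Privacy: "All patients will be identified by a numerical code to ensure pseudo-anonymization". Data Collection and Storage provides one case report form for both clinical and radiographic data, in a database open to the investigators. The reasons for CT in the inclusion criteria are listed as "post-op CT scan available for pain, clicking or contralateral planning".

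**The concern.** Version, inclination, offset and reaming measures depend on where a reader places landmarks and lines. The plan accepts this by testing observer reliability. A reader who knows that a patient had a tenotomy may, without intent, read the scan towards the expected finding. The Introduction already names malpositioned cups among the direct causes, so an expectation exists for at least some measures.

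If several readers share that expectation, the measured groups differ where the true groups do not. The Mann-Whitney test then treats the bias as a predictor, and the reliability results still look good. The stated goal is to guide intraoperative positioning, so a false predictor could reach surgical practice.

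The patient code does not fill the gap. It is described as a means of hiding identity, not group. The CT indication could also hint at group if readers see it.

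**Working it through.** The plan gives no sample size, SD, reader error or reliability target, so there is no figure of its own to reproduce. The check has two parts: whether reliability statistics can see a shared bias, and what such a bias could do to the planned test.

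**Inputs.** From Data Analysis: Mann-Whitney test, significance at 0.05 (two-sided assumed). Assumed, because the plan gives none: between-patient SD 8 degrees (range 6 to 10), reader error SD 2 degrees, shared bias b of 0 to 3 degrees, 30 or 100 patients per group, no true difference.

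**1. Agreement between readers.** Write a reading as X = T + b·G + e, where T is the true value, G is 1 for tenotomy and 0 for control, and e is independent reader error. For two readers of the same scan:

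X1 − X2 = (T + b·G + e1) − (T + b·G + e2) = e1 − e2

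The bias drops out. The same holds for one reader who reads twice knowing the group.

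**2. ICC.** With equal groups, the bias adds b²/4 to the between-patient variance:

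ICC = (SD² + b²/4) / (SD² + b²/4 + error²)

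- b = 0: 64/68 = 0.941
- b = 2: (64 + 1)/(64 + 1 + 4) = 65/69 = 0.942
- Within either group, b is a constant, so ICC = 64/68 = 0.941 for any b.

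Simulation at 30 per group gave 0.939 (b = 0) and 0.940 (b = 2). A test of reader differences by group flagged shared bias in only 4-5% of runs, which is chance. Reliability therefore misses a shared bias both overall and by group.

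**3. False positives in the group comparison, SD 8, b = 2.**

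- SD of a reading: √(64 + 4) = 8.246. Standardised shift: 2/8.246 = 0.2425.
- Noncentrality: λ = 0.2425 × √(n/2) × √(3/π), where 3/π is the Mann-Whitney efficiency under normality and √(3/π) = 0.977.
- n = 30: λ = 0.2425 × 3.873 × 0.977 = 0.918. Rejection = 1 − Φ(1.960 − 0.918) + Φ(−1.960 − 0.918) = 0.149 + 0.002 = 0.151.
- n = 100: λ = 0.2425 × 7.071 × 0.977 = 1.676. Rejection = 1 − Φ(0.284) + Φ(−3.636) = 0.388.

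Simulation (20,000 runs, continuity corrected) gave 0.140 and 0.384.

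**4. Range over the assumptions** (simulated rejection rate, one measure):

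| SD | n per group | b = 0 | b = 1 | b = 2 | b = 3 |
|---|---|---|---|---|---|
| 6 | 30 | 0.047 | 0.088 | 0.209 | 0.415 |
| 6 | 100 | 0.050 | 0.190 | 0.580 | 0.901 |
| 8 | 30 | 0.047 | 0.072 | 0.140 | 0.274 |
| 8 | 100 | 0.049 | 0.129 | 0.384 | 0.704 |
| 10 | 30 | 0.049 | 0.065 | 0.107 | 0.191 |
| 10 | 100 | 0.051 | 0.102 | 0.273 | 0.523 |

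**5. Separate check in SD units.** This used the mean of two readers, error 0.33 SD, group sizes 20/40, 30/30, 50/50 and 30/90, and 3,000 runs each. False positives were 4.5-4.9% with no shift, 14-22% with a shared shift of 0.25 SD and 39-66% with 0.5 SD. ICC over all patients went from 0.90 to 0.904-0.906 at 0.5 SD, and within-group ICC stayed at about 0.90.

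**The case against.** The strongest reply is that this is silence, not error. The reliability sentences are sound as far as they go, nothing in the plan contradicts itself, and masked reading may have been done or intended. That stands, and it limits the point to an omission.

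The size of any bias is also unknown. A 2-degree shift in one direction by every reader equals a full reader-error SD and needs a shared expectation. The Introduction calls the evidence on indirect causes such as offset inconsistent, so the expected direction is less clear there than for cup position. The illustration covers angles only. This stands too: the figures show what the plan would permit, not what is likely here.

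Reliability testing is not useless against observer bias. If only one of two readers is biased, ICC does fall: from 0.90 to 0.85-0.88 at a shift of 0.5 SD, or from 0.94 to 0.93 with a 2-degree shift and SD 8. The gap concerns bias that is shared.

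A reader might infer more than the documents support:

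- That the scans were read unmasked, or that readers saw the clinical fields. Neither is stated.
- That reporting reliability separately by group would close the gap. Step 2 of the working shows that it would not.
- That different prominence thresholds were applied to cases and controls. Materials and Methods can be read as one selection of prominent cups before patients were split by group.

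**Conclusion.** The point holds as an omission that should be corrected. The primary comparison rests on reader-dependent measurements, group is knowable when they are made, and the only stated safeguard cannot detect an error common to the readers. That last statement follows from algebra and needs no assumed figures.

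The size is illustrative only. With the middle assumptions, a shared 2-degree bias moves the false-positive rate per measure from about 5% to about 14-15% at 30 per group and about 38% at 100 per group. Over SD 10 to 6 the ranges are 11-21% and 27-58%. These must not be read as estimates for this study, since SD, reader error, bias and group sizes are all assumed. Masked reading removes this source of bias as far as the masking is effective; in the illustration the rate returns to about 5%.

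**What to change.** Add a short paragraph to Materials and Methods stating that:

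- the readers already planned measure coded scans from both groups in mixed order;
- they do so without group, clinical data or CT indication;
- readings are recorded and locked before they are linked to group.

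If the readings were made this way, saying so settles the matter. If they were made unmasked, re-read the scans masked or report the lack of masking as a limitation.

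The cost is the paragraph and the work of stripping and shuffling scans. The Introduction and Materials and Methods describe scan review in the past tense, while Collected Variables puts reliability testing in the future. The text does not settle whether reading is complete, so some re-reading time may be needed. No extra readers are required. Masking may be incomplete where the image itself reveals the indication, for example contralateral planning, and the paragraph should say so.
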